Correlative Studies Blood Collection	X				X						X			

Trial Period:	Screening Phase	Treatment Cycles ^a (3 weeks per cycle)									Maintenance Period	End of Treatment and Post-Treatment		
Treatment Cycle/Title:	Main Study Screening Visit 1	1	2	3	4	Surgical Period	5	6	7	8+ (to maximum 17 cycles post-op)	End of Treatment (last dose) or Dis-continuation	Safety Follow-up (30 days from last dose)	Survival Follow-Up (phone)	
Scheduling Window (Days):	-28 to -1		± 3	± 3	± 3		± 3	± 3	± 3	± 3		± 7	Every 12 weeks	

a. Unless otherwise specified, assessments/procedures are to be performed prior to dose administration on Day 1 of each cycle.
b. Informed consent for the optional Future Biomedical Research (FBR) samples must be obtained before DNA sample is collected.
c. Refer to Section 5.2.2 regarding window for timing of dose administrations.
d. For women of reproductive potential, a negative pregnancy test should be performed within 72 hours prior to first dose of trial treatment.
e. Laboratory screening tests should be repeated prior to cycle 1 day 1 if the screening labs were performed more than 14 days prior to study treatment.
f. Labs will be collected every other cycle during the maintenance period.
g. First imaging assessment will be performed between at week 11 (+/- 14 days) from study initiation.
h. Second imaging assessment will be performed post-operatively prior to resumption of therapy.
i. Subsequent imaging will be performed every 12 weeks (+/- 7 days) from the timing of the initial post-op imaging test (second imaging assessment).
j. Surgical specimens will be evaluated for pathological response for primary end point analysis.
k. There will be an optional tumor biopsy at the time of disease recurrence.

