7.2.2.7.2 Tumor Imaging During Trial

The first on-study imaging assessment will be performed 11 weeks after Cycle 1 Day 1 (78 days +/- 14 days) and will be used to assess response to chemotherapy and eligibility for surgery. Imaging may be conducted prior to Cycle 4 dosing (of Pembrolizumab) if clinically indicated as assessed by local routine practice. Subsequent imaging will be performed

following surgical resection and will begin within 7 days of Cycle 5 day 1 (first post-operative cycle) which is expected to not be later than 8 weeks from the time of surgery (65 days +/- 14 days). Beginning from the first post-operative scan, subsequent tumor imaging will be performed every 12 weeks (+/- 7 days).

Imaging should continue to be performed until whichever one of the following occurs first:

- disease progression limiting a subject from surgical resection
- recurrence of disease following surgical resection
- completion of study treatment
- withdrawal of consent
- death
- end of study

Imaging should follow calendar days and not be delayed for any dose interruptions that may occur (except for delays post-operatively).

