7.2.2.7.3 Assessment of Disease- RECIST 1.1 and irRECIST

The primary endpoints in this study are recurrence free survival and pathologic surgical response, and not tumor response based on RECIST. In addition due to the neo-adjuvant nature of the study, it is not expected to have confirmatory scans of response prior to surgery. Thus all responses will be unconfirmed and we do not anticipate using irRECIST measurements.

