8.2 Statistical Analysis Plan Details

8.2.1 Efficacy Endpoints

Pathologic complete response (pCR): The number and proportion of subjects with pCR will be reported along with the exact binomial confidence interval. We reject the null that the pCR rate is 3% or less if 3 or more out of the 28 patients achieve pCR.

Disease Free Survival (DFS) and Overall Survival (OS): The Kaplan-Meier method will be used to evaluate all time to event endpoints. Median DFS and OS will be estimated and reported with 95% confidence intervals. Moreover, we will report the estimated DFS at 24 months with 95% confidence intervals.

Overall Response Rate (ORR): The number and proportion of subjects with initial RECIST 1.1 measurable disease who have complete response (CR) or partial response (PR) at any time will be reported along with the exact binomial confidence interval.

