8.2.5.3 Response Criteria

8.2.5.3.1 Evaluation of Target Lesions

Complete Response (CR): Disappearance of all target lesions. Any pathological lymph nodes (whether target or non-target) must have reduction in short axis to <10 mm.

Partial Response (PR): At least a 30% decrease in the sum of the diameters of target lesions, taking as reference the baseline sum diameters.

Progressive Disease (PD): At least a 20% increase in the sum of the diameters of target lesions, taking as reference the smallest sum on study (this includes the baseline sum if that is the smallest on study). In addition to the relative increase of 20%, the sum must also demonstrate an absolute increase of at least 5 mm. (Note: the appearance of one or more new lesions is also considered progressions).

Stable Disease (SD): Neither sufficient shrinkage to qualify for PR nor sufficient increase to qualify for PD, taking as reference the smallest sum diameters while on study.

Progressive Disease (PD): Appearance of one or more new lesions and/or unequivocal progression of existing non-target lesions. Unequivocal progression should not normally trump target lesion status. It must be representative of overall disease status change, not a single lesion increase. Although a clear progression of “non-target” lesions only is exceptional, the opinion of the treating physician should prevail in such circumstances, and the progression status should be confirmed at a later time by the review panel (or Principal Investigator).

Disease recurrence: is defined as PD (as above) or appearance of a new lesion following surgical resection. Evidence of recurrence will generally require biopsy confirmation and the time of recurrence will be the time that biopsy is positive. In situations in which a biopsy is not feasible or recommended by the treating physician or is declined by the subject, the evidence of recurrence will be confirmed by the review panel (or Principal Investigator).

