8.2.5.4 Response Review

All responses will be reviewed by an expert independent of the study at the study's completion. All imaging will be stored at Columbia NYP.

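### The ORR rule sets no pre-operative cut-off, and its denominator is stated in two ways

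*Combined protocol and SAP*

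**What the plan says.** **The rule.** Section 8.1.2 names ORR as a secondary endpoint beside DFS and OS. Section 8.2.1 reports, with an exact binomial interval, the number and proportion of "subjects with initial RECIST 1.1 measurable disease who have complete response (CR) or partial response (PR) at any time".

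**The scans.** Section 7.2.2.7.2 places the first on-study scan 11 weeks after Cycle 1 Day 1 and says that it "will be used to assess response to chemotherapy and eligibility for surgery". Footnote h of the flow chart (6.0) adds: "Second imaging assessment will be performed post-operatively prior to resumption of therapy". Section 7.2.2.7.2 then continues: "Beginning from the first post-operative scan, subsequent tumor imaging will be performed every 12 weeks".

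**What counts as response.** Section 7.2.2.7.3 says that "it is not expected to have confirmatory scans of response prior to surgery. Thus all responses will be unconfirmed". Section 8.2.5.3.1 defines target-lesion CR as "Disappearance of all target lesions", with a size condition for nodes. The same section says that disease recurrence "is defined as PD (as above) or appearance of a new lesion following surgical resection". Section 8.2.5.4 adds: "All responses will be reviewed by an expert independent of the study", to take place when the study is complete. Section 13.3 adopts RECIST 1.1 by reference.

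**Who is counted.** Section 8.2.1, 7.2.2.7.1 and the objective-response line of 8.2.5.1 tie response to measurable disease at baseline. The secondary-outcome line of 8.2.5.1 puts everyone who had one dose into the ORR assessment. The synopsis (Number of Subjects) says that all subjects are available for ORR, and 8.2.4 places all dosed subjects in the secondary efficacy analysis. Section 7.2.2.7.1 states that measurable disease is not needed to pass screening.

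**The concern.** A proportion needs a fixed numerator and a fixed denominator. Here neither is settled.

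The numerator has no time limit, in a trial where most subjects are expected to have the tumour removed part-way through imaging follow-up (the synopsis expects at least 28 of 38 to reach surgery). If a resected target lesion is absent on the first post-operative scan, the protocol's CR wording is met for that lesion because of the operation. No confirmation is required, so one scan is enough. The ORR would then mix drug effect with surgery.

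The denominator is either the measurable subset or everyone dosed, so the same scans can give two different rates. In an open-label, single-arm trial, leaving these choices open until the data are visible allows the result to influence the choice.

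**Working it through.** The documents give no expected ORR, no ORR sample size and no number with measurable disease, so there is no plan figure to reproduce. The check is a comparison of text, followed by illustrative arithmetic.

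**1. Window**

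| Section | What it implies for the time window |
|---|---|
| 8.2.1 | No limit |
| 7.2.2.7.2 | The week-11, pre-operative scan is the one used to judge response |
| 7.2.2.7.3 | Responses are unconfirmed because no second scan is expected before surgery |
| 8.2.5.3.1 | CR has no exception for resected lesions; after resection the defined outcome is recurrence |
| 6.0 footnote h; 7.2.2.7.2 | Scans are taken after resection and every 12 weeks from then on |
| 8.2.5.4 | Independent review, with no window and no rule for resected lesions |

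Three of these point to a pre-operative reading (7.2.2.7.2 on the week-11 scan, 7.2.2.7.3, and the recurrence definition). None states a cut-off. Followed literally, 8.2.1 with the CR definition lets a post-operative scan create a response.

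**2. Denominator**

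| Source | Denominator |
|---|---|
| 8.2.1; 7.2.2.7.1; objective-response line of 8.2.5.1 | Measurable at baseline |
| Secondary-outcome line of 8.2.5.1 (names ORR) | All dosed |
| Synopsis (names ORR); 8.2.4 (does not name it) | All subjects; all dosed |

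The two rules stand together inside 8.2.5.1.

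**3. Size of the denominator conflict**

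Let m be the number measurable, x the responders and N the number dosed. The two rates are x/m and x/N, and x/N = (x/m) × (m/N). They agree only if m = N or x = 0.

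Assumptions: N = 38 (the planned enrolment); a 40% response rate among measurable subjects; m from 15 to 30. Section 8.2.1 gives no confidence level for this interval, so 95% is used. Exact limits are the 0.025 quantile of Beta(x, n − x + 1) and the 0.975 quantile of Beta(x + 1, n − x).

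| m | x | x/m (95% CI) | x/38 (95% CI) |
|---|---|---|---|
| 15 | 6 | 40.0% (16.3 to 67.7) | 15.8% (6.0 to 31.3) |
| 20 | 8 | 40.0% (19.1 to 63.9) | 21.1% (9.6 to 37.3) |
| 25 | 10 | 40.0% (21.1 to 61.3) | 26.3% (13.4 to 43.1) |
| 30 | 12 | 40.0% (22.7 to 59.4) | 31.6% (17.5 to 48.7) |

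At m = 38 there is no difference.

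**4. Size of the window question**

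Each subject scored CR or PR only on a post-operative scan adds 1/m:

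- m = 20: 1/20 = 5.0 points. Two such subjects move 8/20 (40.0%) to 10/20 (50.0%).
- m = 30: 1/30 = 3.3 points. Two such subjects move 12/30 (40.0%) to 14/30 (46.7%).

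The choice of two is only an illustration. The documents do not allow an estimate of the number, and it is zero if post-operative scans are ignored.

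**The case against.** **On the window.** No section states a cut-off that 8.2.1 contradicts. Read beside 7.2.2.7.3, the open time phrase may mean only that a single unconfirmed CR or PR is enough, over the pre-operative scans and over scans in subjects never resected. Scoring a removed lesion as drug response is a strained reading that an independent reviewer would probably reject. RECIST 1.1 is adopted by reference and might already deal with resected lesions; that source was not available for this review.

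Much of this stands as a statement of likely intent. It does not supply the missing rule: 8.2.5.4 gives the reviewer no window, and the point made here is limited to the protocol's own text.

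**On the denominator.** Only 8.2.1 says how the proportion is formed, and a specific rule can be read over a general one. The all-dosed line may mean only that no minimum exposure is required. Moreover, target lesions are drawn from measurable lesions (8.2.5.2) and CR and PR are defined mainly on target lesions, so subjects without measurable disease could hardly be responders; in the all-dosed version they would in effect only enlarge the denominator.

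This makes the measurable-disease reading the likely one, and the fix below adopts it. It does not remove the contradiction, because 8.2.5.1 names ORR under the all-dosed rule and the synopsis names it for all subjects.

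**On consequence.** ORR carries no test, threshold or sample-size role. That is correct and limits the severity.

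**Conclusion.** Both parts hold, as a minor point. The denominator conflict is direct and sits within 8.2.5.1 as well as between sections. The missing cut-off is an inference from three sections that place response before surgery, set against an ORR rule with no limit.

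With 38 dosed and a 40% rate among measurable subjects, the choice of denominator moves the reported ORR from 40% to between 16% and 32% as the measurable number goes from 15 to 30. These counts are assumptions. The effect of the open window cannot be sized beyond 3.3 to 5.0 points per affected subject at 30 or 20 measurable, and may be nil. The analyses of pCR, DFS and OS do not depend on either question.

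**What to change.** - In 8.2.1, replace the open time phrase with best RECIST 1.1 response on scans from Cycle 1 Day 1 to the last scan before resection. For subjects never resected, end the window at progression or new anticancer therapy.
- State that scans after resection inform recurrence and DFS only.
- Use one denominator: dosed subjects with measurable disease at baseline. Report how many of them have no post-baseline scan before resection, and say how they are counted. Treating them as non-responders is a conservative option.
- Bring the synopsis, 8.2.4 and the secondary-outcome line of 8.2.5.1 into line.

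The cost is wording only. The pre-operative scan is already scheduled, so no new imaging is needed. The reported ORR may be lower than under a literal reading of the present rule. Subjects without measurable disease would not count towards ORR, which is already so under 8.2.1 but changes the all-dosed line, and the interval then rests on fewer subjects than an all-dosed one.

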8.2.2 Safety Endpoints

The primary safety objective of this trial is to characterize the safety and tolerability of pembrolizumab in combination with chemotherapy in subjects with gastric cancer. The primary safety analysis will be based on subjects who experienced toxicities as defined by CTCAE criteria. Safety will be assessed by quantifying the toxicities and grades experienced by subjects who have received pembrolizumab, including serious adverse events (SAEs) and events of clinical interest (ECIs).

Safety will be assessed by reported adverse experiences using CTCAE, Version 4.0. The attribution to drug, time-of-onset, duration of the event, its resolution, and any concomitant medications administered will be recorded. AEs will be analyzed including but not limited to all AEs, SAEs, fatal AEs, and laboratory changes. Furthermore, specific immune-related adverse events (irAEs) will be collected and designated as immune-related events of clinical interest (ECIs) as described in Section 7.3.3.2.

8.2.3 Statistical Methods for Safety Analysis

Safety and tolerability will be assessed by clinical review of all relevant parameters including adverse experiences (AEs), laboratory tests, vital signs. Count and percentage of treatment related AEs will be provided. Confidence interval for rate of AE of clinical interest will be estimated using Exact method based on binomial distribution.

8.2.4 Analysis Populations

All subjects who received at least one dose of study treatment will be included in the primary and secondary efficacy and safety analysis.

8.2.5 Measurement of Effect

8.2.5.1 Definitions

Evaluable for toxicity: All patients will be evaluable for toxicity from the time of their first treatment with Pembrolizumab.

Evaluable for primary outcome (pCR):

All subjects who receive a single dose of study medication and are eligible will be considered evaluable for the primary outcome of pCR. Patients who discontinue treatment prior to surgery due to reasons other than eligibility (e.g. disease progression, toxicity, or physician discretion) will be considered as not having achieved pCR. For secondary analysis, we will consider not evaluable those who do not have a pathology report for determination of pCR or discontinue treatment prior to surgery due to reasons other than disease progression and toxicity for the estimation of pCR rate.

Evaluable for secondary outcome (RR, DFS, or OS): All subjects who receive a single dose of study medication will be included in the assessment of ORR, DFS, or OS.

Evaluable for objective response: All patients included in the study must be assessed for response to treatment if they have measurable disease at baseline.

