2.0 TRIAL DESIGN

2.1 Trial Design

This is a non-randomized, multi-site, open-label trial of pembrolizumab and chemotherapy in subjects with gastric or gastroesophageal junction adenocarcinoma. Up to 38 subjects may be enrolled in a single cohort, for a sample of 28 evaluable subjects, to assess the efficacy of combination therapy with standard peri-operative chemotherapy in resectable gastric or GE junction adenocarcinoma. The trial was initiated at 2 sites and two additional sites were subsequently added to increase enrollment.

All study subjects will receive standard of care chemotherapy for 3 cycles prior to and 3 cycles following surgery in combination with Pembrolizumab with an additional cycle of Pembrolizumab (4 total) in the pre-operative period. Additionally, subjects will complete 12 months of maintenance Pembrolizumab (14 additional doses to complete 17 post-operative cycles) following completion of post-operative chemotherapy. The primary efficacy endpoint will be **pathologic complete response (pCR) rate** among all enrolled subjects. Recurrence or disease progression will be determined based on RECIST 1.1 and investigator assessment.

Adverse events will be monitored throughout the trial and graded in severity according to the guidelines outlined in the NCI Common Terminology Criteria for Adverse Events (CTCAE) version 4.0.(As referenced in Appendix 13.2)

After the end of treatment, each subject will be followed for 30 days for adverse event monitoring. Serious adverse events and Events of Clinical Interest (ECI) will be collected for 90 days after the end of treatment or 30 days after the end of treatment if the subject initiates new anticancer therapy, whichever is earlier. Subjects who discontinue treatment for reasons other than disease recurrence will have post-treatment follow-up for disease status until disease recurrence, withdrawing consent, or becoming lost to follow-up. All subjects will be contacted by telephone for overall survival until death, withdrawal of consent or the end of the study, whichever comes first.

[figure not shown]

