5.1.2 Subject Inclusion Criteria

In order to be eligible for participation in this trial, the subject must:

1. Have previously untreated localized gastric or GE junction adenocarcinoma as defined by T2 or greater primary lesion or the presence of any positive nodes- N+(clinical nodes) without evidence of metastatic disease.
2. Plan to proceed to surgery following peri-operative chemotherapy based on standard staging studies per local practice.
3. Be willing and able to provide written informed consent/assent for the trial. The subject may also provide consent for Future Biomedical Research. However, the subject may participate in the main trial without participating in Future Biomedical Research. In cases of partial impairment, impairment that fluctuates over time, or complete impairment due to dementia, stroke, traumatic brain injury, developmental disorders (including mentally disabled persons), serious mental illness, and delirium, a subject may be enrolled if the subject's legally authorized representative consents on the subject's behalf.
4. Be ≥ 18 years of age on day of signing informed consent.
5. Be willing to provide tissue from a newly obtained core or excisional biopsy of a tumor lesion. *Newly-obtained is defined as a specimen obtained up to 6 weeks (42 days) prior to initiation of treatment on Day 1.*
6. Have a performance status of 0 or 1 on the ECOG Performance Scale.
7. Demonstrate adequate organ function as defined in Table 1, all screening labs should be performed within 14 days of treatment initiation.

Table 1 Adequate Organ Function Laboratory Values

System	Laboratory Value
Hematological	
Absolute neutrophil count (ANC)	$\geq 1,500$ /mcL
Platelets	$\geq 100,000$ / mcL
Hemoglobin	≥ 9 g/dL or ≥ 5.6 mmol/L without transfusion or EPO dependency (within 7 days of assessment)
Renal	
Serum creatinine OR	≤ 1.5 X upper limit of normal (ULN) OR

Measured or calculated ^a creatinine clearance (GFR can also be used in place of creatinine or CrCl)	≥ 60 mL/min for subject with creatinine levels $> 1.5 \times$ institutional ULN
Hepatic	
Serum total bilirubin	$\leq 1.5 \times$ ULN OR
	Direct bilirubin \leq ULN for subjects with total bilirubin levels > 1.5 ULN
AST (SGOT) and ALT (SGPT)	$\leq 2.5 \times$ ULN OR ≤ 5 ULN for subjects with liver metastases
Albumin	≥ 2.5 mg/dL
Coagulation	

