In order to confirm eligibility status, Investigators/designees (e.g., study specific Clinical Research Coordinator/Research Nurse, etc.) must submit the following documentation to the Central Registration Office via email or fax:

- The completed/signed study specific Eligibility Checklist (signed by an Physician level Investigator)
- Copies of source documentation necessary for each item to be verified on the CPDM specific Eligibility Checklist, including but not limited to:
 - Copy of required laboratory test and procedure reports (e.g., hematology, serum chemistry, pregnancy test when applicable, MRI reports, CT/bone scans, etc.)
 - Copy of pathology and surgical reports
 - Copy of clinic note(s) or other appropriate medical records capturing the consent process information, along with providing source documentation of any other items needed for screening/eligibility that are not captured in other source document forms (e.g., positive investigator statements of unique eligibility items not captured via other direct source documentation, concomitant medication lists, etc.)
 - Protocol deviation/waiver approvals (if applicable)
- **Please note:** subject line of email or fax should include the protocol number followed by: “Complete Subject Registration Request (PHI)”.

Upon receipt of the above mentioned documentation, participant eligibility information will be verified by a qualified Central Registration Registrar. If any questions arise during the review process, queries in the form of emails will be addressed to the applicable study team personnel for clarification prior to enrollment. All applicable finalized registration/eligibility information will then be entered into HICCC’s institutional CTMS database by the Central Registration Registrar. Upon completion, an official subject registration notification email will be sent to the PI/research team which will include eligibility/enrollment status, as well as subject ID information. Protocol therapy may not be initiated prior to receipt of this notification from the Central Registration Office.

All screen fail/ineligible subjects, as well as subject’s who withdraw consent prior to enrollment/initiation of protocol therapy must be submitted to the Central Registration office in a manner analogous to the procedures noted above. Applicable source documentation will be required within the corresponding submissions.

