10.3 Data and Safety Monitoring Committee

The NCI-approved Data Safety and Monitoring Committee (DSMC) of the Herbert Irving Comprehensive Cancer Center (HICCC) will monitor every subject who receives treatment on this protocol for toxicity. This protocol will adhere to the policies of the currently approved HICCC Data and Safety Monitoring Plan (DSMP), which is in accordance with NCI and CUMC-IRB policy and guidelines. The committee chair is appointed by the HICCC Director. The committee consists of HICCC faculty and staff with expertise in oncology, research pharmacy, research nursing, and data management. The DSMC convenes twice a month to review patient safety and the conduct of the trial. The PI will submit data and safety monitoring reports to the DSMC at a frequency to be determined by the DSMC based on risk to the subjects.

At the time of renewal, the study team will submit the most recent DSMC approval letter for safety review to the CUMC IRB. Any modifications that are required by the DSMC to ensure patient safety will be submitted to the IRB. All protocol deviations, violations, and eligibility waivers will be submitted to and approved by the DSMC prior to being reported to the IRB. All study data reviewed and discussed during these meetings will be kept confidential.

For multicenter research, the principal investigator will assure that there is a mechanism in place to distribute the report to all participating investigators for submission to their local IRB. The report will document that a review of data and outcomes across all centers took place on a given date. It will summarize the DSMC's review of the cumulative toxicities reported from

all participating sites without specific disclosure by treatment arm. It will also inform site investigators of the study the DSMC's conclusion with respect to progress or need for modification of the protocol.

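### Sections 8.2.4, 8.2.5.1 and 2.1 give conflicting denominators for the primary pCR analysis, so a dosed patient later judged ineligible counts as a non-pCR under one section and is excluded under another

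*Combined protocol and SAP*

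**What the plan says.** Three places in the combined protocol and SAP define who is in the primary analysis.

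- Section 8.2.4 (Analysis Populations) sets this rule: "All subjects who received at least one dose of study treatment will be included in the primary and secondary efficacy and safety analysis". There is no eligibility condition.
- Section 8.2.5.1 (Definitions): "All subjects who receive a single dose of study medication and are eligible will be considered evaluable for the primary outcome of pCR". Its failure rule then says that patients who stop before surgery "due to reasons other than eligibility (e.g. disease progression, toxicity, or physician discretion) will be considered as not having achieved pCR". Someone who stops before surgery because of eligibility is outside that rule. The same section sets no eligibility condition for ORR, DFS or OS.
- Section 2.1 (Trial Design): the pCR rate is to be taken "among all enrolled subjects".

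On eligibility itself, section 5.1.2 opens its list of entry criteria with "In order to be eligible for participation in this trial, the subject must", and section 7.1 says that "participant eligibility information will be verified by a qualified Central Registration Registrar" before therapy may start. Section 7.2.2.7.2 uses the word a second time, after dosing: the week-11 scan "will be used to assess response to chemotherapy and eligibility for surgery". Section 10.3 provides for exceptions: "All protocol deviations, violations, and eligibility waivers will be submitted to and approved by the DSMC".

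The decision rule in sections 8.1.1 and 8.2.1 is 3 or more pCRs out of 28, for 3% against 15%, one-sided. Up to 38 subjects may be enrolled.

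**The concern.** A dosed but ineligible patient cannot be handled under both 8.2.4 and 8.2.5.1. This is a contradiction about the primary endpoint's denominator, not a missing detail. Section 2.1 adds a further difference, since a subject can be enrolled and never dosed.

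Section 8.2.5.1 also leaves the excluding term loose. It does not cite section 5.1, sets no date by which ineligibility must have been evident, and names nobody to decide. Suppose metastases or unresectable disease come to light at the week-11 scan or at exploration. The case can be recorded as progression, which is a non-pCR, or as disease missed at baseline that breached the first inclusion criterion, which removes the patient. The text gives no rule for choosing. Such a patient cannot have a T0N0 specimen, so removal can only raise the pCR rate. The trial is open-label with a single arm, so nothing in the design conceals outcome from whoever makes that choice.

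**Working it through.** **Inputs.** From section 8.1.1: null rate 3%, alternative 15%, one-sided binomial test, reject at 3 or more of 28, 38 enrolled. The number of dosed patients who might be called ineligible is not in the documents. I assume 2 to 4 removals, all of them non-pCR, and 3 observed pCRs.

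**Formula.** P(X ≥ 3 | n, 0.03) = 1 − Σ C(n,k)·0.03^k·0.97^(n−k), summed over k = 0, 1, 2.

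**The plan's own figure.** At n = 28 the three terms are 0.4262, 0.3691 and 0.1541, which sum to 0.9494, so alpha is 0.0506. Power at 15% is 0.813. The stated 80% power is reproduced. The stated alpha of 0.05 holds to two decimals and is slightly exceeded.

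**Effect of the denominator with 3 pCRs.**

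| Dosed | Removed | Analysed | pCR rate | One-sided p |
|---|---|---|---|---|
| 38 | 0 | 38 | 3/38 = 7.9% | 0.105 |
| 38 | 2 | 36 | 3/36 = 8.3% | 0.093 |
| 38 | 4 | 34 | 3/34 = 8.8% | 0.081 |
| 30 | 0 | 30 | 3/30 = 10.0% | 0.060 |
| 30 | 2 | 28 | 3/28 = 10.7% | 0.0506 |

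With 38 dosed, removing 2 to 4 shifts the estimate by 0.4 to 0.9 percentage points and leaves p well above 0.05. With 30 dosed, the exact test on all dosed needs 4 pCRs (alpha 0.060 for 3 or more, 0.012 for 4 or more). Removing 2 brings the analysis to 28, where the plan's rule needs only 3.

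**Rule at the full sample.** At n = 38, 3 or more has alpha 0.105 and 4 or more has alpha 0.027. Power for 4 or more is 0.842 if the 15% applies to all dosed. If 15% applies only to the 28 of 38 expected to reach surgery, the rate among all dosed is 0.15 × 28/38 = 11.1% and power is 0.618.

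**The case against.** A reader might infer that treatment failures can be removed freely once the outcome is known. The documents do not support that.

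- Eligibility is a baseline concept almost everywhere. Section 7.2.5.1 has the entry requirements checked within 28 days before therapy, the flow chart marks inclusion/exclusion review at screening only, and section 7.2.3.1 says laboratory tests repeated on Cycle 1 Day 1 do not bear on eligibility. Central verification precedes the first dose.
- Section 8.2.5.1 itself names progression, toxicity and physician discretion as non-pCR. New lesions are progression under section 8.2.5.3.1.
- A reader might take the week-11 wording to mean that patients who become unresectable are ineligible and so drop out. But section 7.2.2.7.2 qualifies the word as eligibility for surgery, and the same section describes progression as the thing that prevents resection.
- Waivers are listed only where applicable, and section 13.4 requires affiliate sites to obtain them prospectively. They are pre-dose facts, and the documents do not say that such patients are expected.
- The exclusion is neutral in form: an ineligible patient with a pCR would be dropped too.
- Removing failures adds no pCRs, so it cannot turn fewer than 3 into a rejection under the stated rule.

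A reader might also calculate the effect of removing all 10 patients not expected to reach surgery. That is implausible given the failure rule, and most of the resulting shift comes from a rule fixed at 28 when up to 38 may be dosed.

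All of this stands, and it narrows the exposure. It does not reconcile the sections. If registration settled eligibility for good, there would be no need to provide for patients who stop before surgery because of it, yet 8.2.5.1 does so. A natural source is section 5.8, which allows withdrawal when enrolment proves inappropriate, but no cross-reference says so.

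**Conclusion.** The contradiction is certain and should be resolved before analysis. The bias is only possible, and its route is narrow: disease found after dosing and reclassified as a baseline breach. No passage says that this is intended.

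The size is modest. With 38 dosed, the assumed 2 to 4 removals would not change the conclusion of an exact test at the actual n. It could matter when slightly more than 28 are dosed, as in the 30-patient case. These figures rest on 3 observed pCRs, on removed patients all being non-pCR, and on an assumed number of removals. They also assume that the test is applied to the number actually analysed; the plan gives a rejection count only for 28.

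**What to change.** - In section 8.2.5.1, delete the eligibility condition from the definition of evaluable for pCR and the eligibility carve-out from the failure rule. The primary set is then every registered subject with at least one dose, as in 8.2.4, and any such subject without a confirmed T0N0 specimen is a non-pCR.
- Align section 2.1 with that set.
- Report an eligible-only pCR rate as a sensitivity analysis. Limit ineligibility to breaches of section 5.1 shown by data dated before Cycle 1 Day 1 and documented without reference to response. State that unsuitability for surgery is not ineligibility.
- State the rejection count for the actual number analysed; for example, at n = 38, at least 4 pCRs (exact alpha 0.027).

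A lighter alternative would keep the eligible-only set as primary, with a citation of 5.1 and a pre-dose date limit. That would narrow the relabelling route, but 8.2.4 and 2.1 would then have to be rewritten to match.

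The cost is wording only. A genuinely misregistered patient stays in as a likely non-pCR, so the estimate may be slightly lower. Restating the count also exposes the power question shown above: 0.842 or 0.618 at n = 38, depending on whether the 15% refers to all dosed or only to those resected.
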